2.8.4 Other safety data

2.8.4.1 ECG and cardiac imaging data

ECG Data handling

In case the study requires ECG replicates at any assessment, the average of the ECG parameters at that assessment should be used in the analyses.

ECG Data analysis

Standard 12-lead ECGs including PR, QRS, QT, QTcF, and HR intervals will be obtained local for each patient during the study. ECG data will be read and interpreted locally.

The number and percentage of patients with notable ECG values will be presented:

- QT, QTcF
 - New value of > 450 and ≤ 480 ms
 - New value of > 480 and ≤ 500 ms
 - New value of > 500 ms
 - Increase from Baseline of $> 30 \text{ ms to} \le 60 \text{ms}$
 - Increase from Baseline of > 60 ms
- PR
 - Increase from baseline >25% and to a value >200 ms
 - New value of > 200 ms
- QRS
 - Increase from baseline >25% and to a value > 120 ms
 - New values of QRS > 120 ms

The normal range for HR is displayed in Table 2-11 Recommendation for normal heart rate per age group and gender. The number and percentage of patients with notable values will be presented.

						-	-	-	
Age group	0-1 month	1-3 months	3-6 months	6-12 months	1-3 years	3-5 years	5-8 years	8-12 years	12-18 years
HR (bpm) Boys	(125, 190)	(125, 185)	(110, 165)	(105, 165)	(95, 155)	(75, 125)	(60, 115)	(55, 100)	(50, 100)
HR (bpm) Girls	(135, 215)	(125, 200)	(120, 190)	(105, 185)	(95, 180)	(80, 125)	(70, 115)	(60, 110)	(50, 100)
Detection in the foregraph laws limited and the UD, he adopted a foregraph									

Table 2-11	Recommendation for normal heart rate per age group and gender
	recommendation for normal near rate per age group and genaer

Data shown as upper limit of normal, lower limit of normal for HR= heart rate. Ref.: adapted from Rijnbeek et al. 2001.

The summaries will include all ECG assessments performed no later than 30 days after the last date of study drug. A listing of all ECG assessments will be produced and notable values will be flagged. A separate listing of only the patients with notable ECG values may also be produced. In the listings, the assessments collected during the post-treatment period will be flagged.

The denominator to calculate percentages for each category is the number of patients with both a baseline and a post-baseline evaluation. A newly occurring post-baseline ECG notable value is defined as a post-baseline value that meets the criterion post-baseline but did not meet the criterion at baseline.

For each ECG parameter, descriptive statistics at baseline, at each post-baseline time point and changes from baseline at each post-baseline time point will be summarized. Descriptive statistics at worst post-baseline and changes from baseline to worst post-baseline will also be summarized separately.

For each of the QTc and QT intervals, shift tables based on notable parameter categories (<450, 450-<481, 481-<501, ≥501 ms) at baseline and the worst post-baseline value observed.

Frequency counts and percentages of patients with newly occurring post-baseline qualitative ECG abnormalities (morphology) will be summarized. The denominator to calculate percentages is the number of patients with both a baseline and a post-baseline evaluation. A newly occurring post-baseline qualitative ECG abnormality is defined as a post-baseline abnormal finding which was not present at baseline.

Patients with notable ECG interval values and newly occurring qualitative ECG abnormalities will be listed and the corresponding notable values and abnormality findings will be included in the listings.

Unscheduled ECG measurements will not be used in computing the descriptive statistics for change from baseline at each post-baseline time point. However, they will be used in the analysis of notable ECG changes and the shift table analysis of notable QT parameters.

ECHO Data handling

ECHO data will be analyzed based on local reported results. The summaries will include all ECHO assessments performed no later than 30 days after the last date of study drug. All ECHO

Novartis	Confidential	Page 42
SAP	30-Sep-2021 (6:19)	CDRB436G2201

assessments will be listed, and those collected later than 30 days after study drug discontinuation will be flagged in the listing.

The same modality (ECHO or MUGA) for determining cardiac scan data (e.g., left ventricular ejection fraction (LVEF)) should be used to follow a patient throughout the study. The absolute change from baseline values will not be calculated for any patients where the post-baseline value was determined by a cardiac scan modality that is different than the one used to determine baseline value.

ECHO Data analysis

Absolute change from baseline in LVEF will be summarized in the worst case post-baseline. Only the post-baseline assessments that used the same method (ECHO or MUGA) as the baseline assessments will be used to derive the change from baseline. The change from baseline will be categorized as follows:

- No change or any increase
- Any decrease:
 - \circ > 0 <10% Decrease
 - 10 <20% Decrease
 - $\circ \geq 20\%$ Decrease
- $\geq 10\%$ decrease and $\geq LLN$
- $\geq 10\%$ decrease and < LLN
- $\geq 20\%$ decrease and $\geq LLN$
- $\geq 20\%$ decrease and < LLN

ECHO assessments of LVEF will be listed for each patient including absolute change from baseline at each assessed time interval. The values of potential clinical importance will also be flagged.

2.8.4.2 Vital signs

Vital sign assessments are performed in order to characterize basic body function. The following parameters are being collected: height (cm), weight (kg), body temperature (°C), pulse rate (beats per minute), systolic and diastolic blood pressure (mmHg).

Data handling

Vital signs collected on treatment will be summarized. Values measured outside of on treatment period will be flagged in the listings.

Data analysis

For analysis of vital signs the clinically notable vital sign criteria are provided in Table 2-12 Criteria for notably abnormal vital signs below.

		Clinically no	table criteria		
Vital sign (unit)	Hi	gh	Lo	W	
Systolic blood pressure [mmHg]	≥ 95th percentile height group¹	≥ 95th percentile of the age and height group ¹		of the age and	
Diastolic blood pressure [mmHg]	≥ 95th percentile height group ¹	≥ 95th percentile of the age and height group ¹		≤ 5th percentile of the age and height group ¹	
Body temperature [°C]	≥ 38	.4°C	≤ 35	.0°C	
Pulse rate [bpm] ²	12-18 months	> 140	12-18 months	< 103	
	18-24 months	> 135	18-24 months	< 98	
	2-3 years	> 128	2-3 years	< 92	
	3-4 years	> 123	3-4 years	< 86	
	4-6 years	> 117	4-6 years	< 81	
	6-8 years	> 111	6-8 years	< 74	
	8-12 years	> 103	8-12 years	< 67	
	12-15 years	> 96	12-15 years	< 62	
	≥ 15 years	> 92	≥ 15 years	< 58	
Weight	increase from baseline³ of ≥ 2 BMI-for-age percentile categories⁴		decrease from b BMI-for-age per categories ⁴		

Table 2-12Criteria for notably abnormal vital signs

bpm=beats per minute; CDC= Centers for Disease Controls and prevention; NHLBI= National Heart, Lung, and Blood Institute;

¹ Blood pressure percentiles are calculated for each blood BP record using the method described in Appendix B of the following reference: The Fourth Report on Diagnosis, Evaluation and Treatment of High Blood Pressure in Children and Adolescents. Pediatrics 2004; 114; 555.

Note: Methods applies to patients less than 3 years old.

² Fleming S, Thompson M, Stevens R, et al. Normal ranges of heart rate and respiratory rate in children from birth to 18 years of age: a systematic review of observational studies. Lancet 2011; 377: 1011-18.

³ Baseline BMI-for-age weight status categories are underweight (less than the 5th percentile), healthy weight (5th percentile to less than the 85th percentile), overweight (85th to less than the 95th percentile) and obese (equal to or greater than the 95th percentile);

⁴ BMI-for-age percentiles categories (P3, P5, P15, P25, P50, P75, P85, P95, P97) are obtained from the WHO Growth Charts (http://www.who.int/childgrowth/en/);

Note: For patients less than 2 years old, growth charts are based on recumbent length instead of height, which is not collected in the study. As an approximation, height collected in the study is considered as equal to the recumbent length; for patients over 228 months- old, percentiles are not available and will be considered as missing.

The number and percentage of patients with notable vital sign values (high/low) will be presented.

Vital signs shift table based on values classified as notable low, normal, notable high or notable (high and low) at baseline and worst post-baseline will be produced for pulse rate, diastolic BP and systolic BP. Baseline is defined as the last non-missing value prior to or coinciding with first dose. The worst post-baseline value refers to the worst post-baseline value on treatment.

Novartis	Confidential	Page 44
SAP	30-Sep-2021 (6:19)	CDRB436G2201

Descriptive statistics (mean, median, standard deviation, minimum and maximum) will be tabulated for baseline, at each post-baseline time point and changes from baseline at each post-baseline time point for each vital sign measure. For each parameter, only patients with a value at both baseline and post baseline (on treatment) will be included.

A listing of all vital sign assessments will be produced by and notable values will be flagged. A separate listing of only the patients with notable vital sign values may also be produced. In the listing, the assessments collected outside of on-treatment period will be flagged.

2.8.4.3 **Performance status**

The Karnofsky and Lansky performance status scale (Table 2-13 Performance status criteria) will be used to assess physical health of patients:

Table 2-13	Performance status criteria

PERFORMANCE STATUS CRITERIA					
Karnofsky and Lansky performance scores are intended to be in multiples of 10					
Karnof	sky (age >16 years of age)	Lansky	/ (age <16 years)		
Score	Description	Score	Description		
100	Normal, no complaints no evidence of disease.	100	Fully active, normal.		
90	Able to carry on normal activity, minor signs of symptoms of disease.	90	Minor restrictions in physically strenuous activity.		
80	Normal activity with effort, some signs of symptoms of disease.	80	Active, but tires quickly.		
70	Cares for self, unable to carry on normal activity or do active work.	70	Both greater restriction of and less time spent in play activity.		
60	Requires occasional assistance, but is able to care for most of his/her needs.	60	Up and around, but minimal active play, keeps busy with quieter activities.		
50	Requires considerable assistance and frequent medical care.	50	Gets dressed, but lies around much of the day; no active play, able to participate in all quiet play and activities.		
40	Disabled, requires special care and assistance.	40	Mostly in bed, participates in quiet activities.		
30	Severely disabled, hospitalization indicated. Death not imminent.	30	In bed, needs assistance even for quiet play.		
20	Very sick, hospitalization indicated. Death not imminent.	20	Often sleeping; play entirely limited to very passive activities.		
10	Moribund, fatal processes progressing rapidly.	10	No play, does not get out of bed.		

[figure not shown]
Frequency counts and percentages of patients in the score category of 100, 90, 80, 70, and < 70 will be provided by time point based on the windows defined in Section 2.1.1. A summary of change from baseline by scheduled visits will be performed, as well as the worst case post-baseline and the best case post-baseline changes during the study.

Novartis	Confidential	Page 45
SAP	30-Sep-2021 (6:19)	CDRB436G2201

A supporting listing will also be provided.

2.8.4.4 Dermatological Evaluation

Skin examination results will be summarized by frequency counts and percentages of patients in each category (normal, abnormal) by scheduled time points. A supporting listing will also be provided.

2.8.4.7 Growth and development (Height and Weight)

Growth data consist of height, weight, BMI, height velocity and weight velocity.

Novartis	Confidential	Page 46
SAP	30-Sep-2021 (6:19)	CDRB436G2201

Height and BMI will be summarized at 6-month intervals, using the standard deviation scores (SDS, also called z-score), velocity and velocity SDS. The relevant height and weight values for each 6-month period are defined using time windows, as defined in Table 5-3. The z-scores will allow identification of potential outliers.

The formula used to calculate the SDS and height and weight velocities are provided in the Appendix 5.3.2.

Note that BMI SDS are reported instead of weight SDS as no reference data for weight are provided by the WHO for age beyond 10.

Height and BMI SDS and heigh and weight velocity SDS will be summarized using descriptive statistics (mean, standard deviation, range) for each time window (at Baseline and thereafter allowing informal comparison of growth data), as well as by presenting number of patients with SDS values lower/higher than 5th/95th percentiles respectively.

Box plots will be plotted for each time window. A shift table to compare baseline SDS to the worst on-treatment SDS categorized as Low (SDS <- 1.645), High (SDS > 1.645) or Normal (- $1.645 \le SDS \le 1.645$) will be produced for height and BMI SDS. Another shift table to compare the baseline height SDS to the last available on-treatment height SDS categorized according to the main percentile lines (>95th, 95th to 90th, 90th to 75th, 75th to 50th, 50th to 25th, 25th to 10th, 10th to 5th and \le 5th percentile) will be produced. All height and BMI SDS, velocity and velocity SDS data will be listed, and values of SDS and velocity SDS outside of the central 95% of population values will be flagged as either High (SDS > 1.645) or Low (SDS <- 1.645).

2.8.4.8 Ophthalmologic exam

Visual acuity will be converted from snellen to logMAR scale as defined in Holladay 1997 (20), and categorized as the following change from baseline:

- Improvement: $\geq 0.2 \log MAR$ improvement (decrease in logMAR)
- Stable: neither ≥ 0.2 logMAR improvement nor worsening, where
- Worsening: $\geq 0.2 \log$ MAR worsening (increase in logMAR)

Visual acuity categories at each time point, as well as best and worst category on treatment will be presented. Data

from ophthalmologic exams will be listed.

2.8.4.10 Palatability

Data on palatability assessments for dabrafenib and trametinib oral solutions (bitterness, sweetness, texture and overall taste) will be summarized and listed.

2.8.4.11 Additional analyses

Time to first occurrence

Time to first occurrence of an event is defined as time from start of study treatment to the date of first occurrence of this event (or first event within an AE grouping), i.e. time in days is calculated as (start date of first occurrence of event) – (start of study treatment) +1.

Page 47

For Kaplan-Meier analyses of time to occurrence, in the absence of an event during the ontreatment period, the censoring date applied will be the earliest of the following dates:

- death date •
- new anticancer antineoplastic therapy start date •
- end date of on-treatment period •
- data cut-off date
- withdrawal of informed consent date.

Failure curves (ascending Kaplan-Meier curves) will be constructed. Median together with 95% confidence interval as well as 25th percentile and 75th percentile will be presented.

In addition, the median time to occurrence for the subset of patients who experienced the event of interest will be calculated. Simple descriptive statistics, median, min and max as well as 25th percentile and 75th percentile, will be presented.

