For safety and efficacy evaluations, the last available assessment on or before the date of start of study treatment is defined as "baseline" assessment. In the rare case that time of assessment and time of treatment start is captured, the last available assessment before the treatment start date/time is used for baseline.

If patients have no value as defined above, the baseline result will be missing.

On-treatment assessment/event and observation periods

For safety reporting the overall observation period will be divided into three mutually exclusive segments:

- 1. *pre-treatment period*: from day of patient's informed consent to the day before first administration of study treatment
- 2. *on-treatment period*: from date of first administration of study treatment to 30 days after date of last actual administration of any study treatment (including start and stop date)
- 3. *post-treatment period*: starting at day 30+1 after last administration of study treatment.

Notes: if data on clock time is available in the clinical database (e.g. for time of blood/urine sample taken, ECG performed, etc. and first study treatment administration), a more precise distinction between pre-treatment and on-treatment periods is encouraged to be used. If dates are incomplete in a way that clear assignment to pre-, on-, post-treatment period cannot be made, then the respective data will be assigned to the on-treatment period.

Safety summaries (tables, figures) include only data from the on-treatment period with the exception of baseline data which will also be summarized where appropriate (e.g. change from baseline summaries). In addition, a separate summary for death including on treatment and post treatment deaths will be provided. In particular, summary tables for adverse events (AEs) will summarize only on-treatment events, with a start date during the on-treatment period (*treatment-emergent* AEs).

However, all safety data (including those from the post-treatment period) will be listed and those collected during the pre-treatment and post-treatment period will be flagged.

Novartis	Confidential	Page 14
SAP	30-Sep-2021 (6:19)	CDRB436G2201

Windows for multiple assessments

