2.4.2 Prior, concomitant, on study and post therapies

Prior anti-cancer therapy

The number and percentage of patients who received any prior anti-neoplastic medications, prior anti-neoplastic radiotherapy or prior anti-neoplastic surgery will be summarized. Prior anti-neoplastic medications will be summarized by therapy type (e.g. chemotherapy, hormonal therapy etc.), setting (e.g. adjuvant, metastatic, etc.) and also by lowest ATC class and preferred term. Summaries will include total number of regimens, best response and time from last treatment to progression for the last therapy. The medication therapy type of any combination therapy will be classified based on the following order: chemotherapy, biologic therapy, targeted therapy, hormonal therapy. For example, a combination therapy of chemotherapy and hormonal therapy will be classified as 'chemotherapy'. For radiotherapy, time since last radiotherapy, locations and setting of last therapy will be summarized. For prior surgery, time since last surgery, procedure and residual disease of last therapy will be summarized.

Separate listings will be produced for prior anti-neoplastic medications, radiotherapy, and surgery.

Anti-neoplastic medications will be coded using the WHO Drug Dictionary (WHO-DD); antineoplastic surgery will be coded using MedDRA. Details regarding MedDRA and WHO-DD version will be included in the footnote in the tables/listings.

The above analyses will be performed using the FAS.

On-study Radiotherapy and Surgery

As on study radiotherapy is allowed after centrally confirmed radiologic progression of disease or at least a total of 36 months of treatment plus follow-up, whichever comes first, surgeries and radiotherapies occurring on study will be listed only.

For patients enrolled in the HGG cohort, anti-cancer surgery is allowed for patients enrolled on the study after at least 8 months on treatment or after radiologic progression of disease has been confirmed by investigator. Study treatment may be taken up to one day prior to surgery as deemed appropriate by the investigator.

Post treatment anti-cancer therapy

Anti-neoplastic therapies since discontinuation of study treatment will be listed and summarized by ATC class, preferred term, and by means of frequency counts and percentages using FAS. In addition, listings will include best response to the regimen.

Concomitant medications

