New anticancer therapy (including cancer related surgery and radiotherapy) given prior to protocol defined progression	Date of last adequate assessment on or prior to starting new anti-cancer therapy	Censored

Table 2-9Outcome and event/censor dates for DOR and PFS analysis

Novartis	Confidential	Page 34
SAP	30-Sep-2021 (6:19)	CDRB436G2201

Situation	Date	Outcome	
Death before first PD	Date of death	PFS event	
assessment			

* This refers to undocumented progression based on investigator claim only. Clinical Status will be considered as appropriate in the determination of progression per RANO criteria.

Censoring pattern of PFS

Number of patients with a PFS event and number of patients censored for the PFS analysis will be summarized. In addition, a summary of reasons for PFS censoring will be provided by based on the following reasons:

- 1: Ongoing without event
- 2: Lost to follow-up
- 3: Withdrew consent
- 4: Adequate assessment no longer available
- 5: Initiation of new cancer therapy prior to progression
- 6: Event after >=2 missing tumor assessments

The PFS censoring reasons are defined in the following way.

If the time interval between the last adequate TA date and the earliest of the following dates is smaller or equal to interval of 2 missing tumor assessments (see Section 2.7.3 for definition):

- 1. Analysis cut-off date,
- 2. Start date of further anti-neoplastic therapy,
- 3. Date of consent withdrawal,
- 4. Visit date of study treatment discontinuation or end of post-treatment follow-up discontinuation due to lost to follow-up.

Then the PFS censoring reason will be:

- 1. 'Ongoing',
- 2. 'New cancer therapy added',
- 3. 'Withdrew consent',
- 4. 'Lost to follow-up',

If the time interval is larger than the interval of 2 missing tumor assessments with no event observed, then the PFS censoring reason will always default to 'Adequate assessment no longer available'. If the time interval between the last adequate tumor assessment date and the PFS event date is larger than the interval of 2 missing tumor assessments then the patient will be censored and the censoring reason will be 'Event documented after two or more missing tumor assessments'.

These summaries on censoring reasons will be produced for PFS by investigator and central independent reviewers. The censoring patterns will be compared between investigator and central independent reviewers.

Novartis	Confidential	Page 35
SAP	30-Sep-2021 (6:19)	CDRB436G2201

OS

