2.8.1.1 Adverse events of special interest / grouping of AEs

All AE groupings for a clinical program are stored in the Compound Case Retrieval Strategy sheet (CRS) with clear versioning and reference to the MedDRA version used.

All AESI definitions or AE grouping need to be specified in the CRS. If a CRS update is necessary, the final version needs to be available in a reasonable time ahead of the DBL. The CRS version should be included in a footnote of the AESI tables.

Data analysis of AESIs

An adverse event of special interest is a grouping of adverse events that are of scientific and medical concern specific to dabrafenib and trametinib. These groupings are defined using MedDRA terms, SMQs (standardized MedDRA queries), HGLTs (high level group terms), HLT (high level terms) and PTs (preferred terms). Customized SMQs (Novartis MedDRA queries, NMQ) may also be used. A NMQ is a customized group of search terms which defines a medical concept for which there is no official SMQ available or the available SMQ does not completely fit the need. It may include a combination of single terms and/or an existing SMQ, narrow or broad. For each specified AESI, number and percentage of patients with at least one event of the AESI occurring during on treatment period will be summarized.

AESI for dabrafenib and trametinib are:

- Skin related toxicities
- Ocular events
- Cardiac related events
- Hepatic disorders
- Pneumonitis/interstitial lung disease
- Bleeding events
- Hypertension

- Pyrexia
- Pre-Renal and intrinsic renal failure
- Uveitis
- New primary /secondary malignancy
- Hypersensitivity
- Hyperglycemia
- Venous thromboembolism
- Pancreatitis
- Neutropenia

Summaries of these AESIs will be provided by dabrafenib and trametinib, (specifying grade, SAE, relationship, leading to treatment discontinuation, leading to dose adjustment/interruption, fatal outcome, etc.). If sufficient number of events occurred, analysis of time to first occurrence will be applied.

A listing of all grouping levels down to the MedDRA preferred terms used to define each AESI will be generated.

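### Both 2021 SAPs censor time to first AESI at new anticancer therapy only for event-free patients, which biases the Kaplan-Meier curve upward, usually by a small amount

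*SAP*

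**What the plan says.** The HGG SAP Amendment 2 and the LGG SAP Amendment 1 carry the same rule in section 2.8.4.11 (Additional analyses).

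- **Event:** "Time to first occurrence of an event is defined as time from start of study treatment to the date of first occurrence of this event". Nothing removes an event that begins after new anticancer therapy.
- **Censoring:** "in the absence of an event during the ontreatment period, the censoring date applied will be the earliest of the following dates". The five dates are death, "new anticancer antineoplastic therapy start date", end of the on-treatment period, data cut-off and withdrawal of consent.
- **Window:** section 2.1.1 of both SAPs defines the on-treatment period as running "from date of first administration of study treatment to 30 days after date of last actual administration of any study treatment". AE tables "will summarize only on-treatment events, with a start date during the on-treatment period". New therapy does not shorten this period. The one exception is in the LGG SAP: for a crossover that starts within 30 days of the last dose, the period ends the day before the first crossover dose.
- **Trigger:** section 2.8.1.1 says "If sufficient number of events occurred, analysis of time to first occurrence will be applied".

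The 2023 final-analysis SAPs keep the analysis (HGG section 2.8.4.10, LGG section 2.8.4.11). They list only death, end of the on-treatment period, cut-off and consent withdrawal.

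**The concern.** Kaplan-Meier needs the decision to censor at a given time to be independent of what happens to the patient afterwards. Here it is not. Whether a patient is censored at the start of new therapy is settled by looking ahead to see if an AESI occurs later in the on-treatment period. Among patients who have started new therapy, only those who will go on to have an event stay in the risk set; the event-free ones have been removed.

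The ascending curve and its median and quartiles therefore point to higher and earlier AESI risk than the data support. This differs from the usual debate about censoring at death or end of treatment, since it would arise with no deaths at all. It also means that the primary and final time-to-onset outputs follow different rules, so they should not be compared without saying so.

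**Working it through.** The SAPs give no figure for this analysis, so there is none to reproduce. The check has three steps.

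**1. What each rule does.** Take a patient who starts new therapy on day s, with the on-treatment period ending on day E > s, and no earlier death, cut-off or consent withdrawal.

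| Outcome | Rule as written (L) | A: entry deleted (2023 SAPs) | B: new therapy ends follow-up for all |
|---|---|---|---|
| AESI at t ≤ s | event at t | event at t | event at t |
| AESI at s < t ≤ E | event at t | event at t | censored at s |
| No AESI by E | censored at s | censored at E | censored at s |

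L takes its second row from A and its third row from B. A and B each apply one window to everyone; L does not.

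**2. Direction.** L and A count the same events at the same times. At an event time t, let r be the number at risk under A. Let c be the number of event-free patients who have started new therapy before t and whose on-treatment period is still running. The Kaplan-Meier factor for one event is 1 − 1/r under A and 1 − 1/(r − c) under L. Since r − c ≤ r, the factor under L is never larger, and it is smaller whenever c > 0. The failure curve under L therefore lies at or above that under A in every data set. This needs no assumption about hazards. The comparison with B does assume that new therapy leaves the AESI hazard unchanged.

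**3. Size.** Simulation with N = 40 (the planned HGG enrolment) and 4,000 replicates per scenario.

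Assumptions, none of them from the SAPs:
- AESI hazard of 0.03 or 0.10 per month, unchanged by new therapy.
- Exponential time on treatment with mean 4 or 12 months, capped at 24.
- 30% or 70% of patients start new therapy, 1 to 30 days after the last dose.

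True 12-month incidence is 1 − exp(−0.03 × 12) = 30.2% or 1 − exp(−0.10 × 12) = 69.9%. Mean estimates at 12 months, in percent:

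| Hazard | Mean months on treatment | New therapy | L | A | B | L − A | L − B |
|---|---|---|---|---|---|---|---|
| 0.03 | 4 | 30% | 30.9 | 30.1 | 30.2 | 0.8 | 0.7 |
| 0.03 | 4 | 70% | 31.4 | 29.5 | 29.7 | 1.9 | 1.7 |
| 0.03 | 12 | 30% | 30.4 | 30.1 | 30.1 | 0.3 | 0.3 |
| 0.03 | 12 | 70% | 30.7 | 30.0 | 30.1 | 0.7 | 0.6 |
| 0.10 | 4 | 30% | 69.0 | 68.0 | 67.9 | 1.0 | 1.1 |
| 0.10 | 4 | 70% | 70.0 | 67.5 | 67.3 | 2.5 | 2.7 |
| 0.10 | 12 | 30% | 70.2 | 69.8 | 69.8 | 0.4 | 0.4 |
| 0.10 | 12 | 70% | 70.8 | 69.8 | 69.9 | 1.0 | 0.9 |

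The excess is 0.3 to 2.5 points against A and 0.3 to 2.7 against B. L was at or above A in every replicate. With a mean of 4 months on treatment, few of 40 patients are still at risk at 12 months and the curves flatten early. The fair comparison is therefore between rules, not with the true value.

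**The case against.** The strongest case against the point is that it is small and largely overtaken. The 2023 SAPs govern the final analysis and have removed the date. The output is descriptive, is produced only if enough events occur, and feeds no decision rule. For scale, the exact 95% interval around 30% with 40 patients is 16.6% to 46.5% (HGG SAP Amendment 2, Table 3-1), far wider than the bias. All of this stands, and it limits the weight of the point. It does not make the 2021 rule valid for the analyses run under it.

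A reader might infer a much larger bias by treating on-study surgery or radiotherapy as new therapy during continued dosing. There is wording that invites this. The HGG table of DOR and PFS censoring has "New anticancer therapy (including cancer related surgery and radiotherapy) given prior to protocol defined progression", and section 2.4.2 says "anti-cancer surgery is allowed for patients enrolled on the study after at least 8 months on treatment". Letting new therapy start during dosing in the same simulation raises the excess to about 3 to 17 points. The documents do not support that as the expected size:

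- The parenthesis belongs to DOR and PFS, and the similar mention of surgery in section 2.5.1 belongs to best overall response. Section 2.8.4.11 refers to neither.
- Section 1.1 lists a new anti-neoplastic therapy among the reasons study treatment ends. The long gap needs surgery to count as new therapy for censoring but not for stopping.
- On-study radiotherapy is tied to confirmed progression or 36 months, not to month 8. In the LGG cohort the same holds for surgery.

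Two further inferences go too far. The risk set as a whole is not made up only of future events, since patients who have not started new therapy remain in it. A difference from the AESI count tables is no proof of error either, because Kaplan-Meier estimates and crude percentages differ under any censoring.

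**Conclusion.** The point holds for section 2.8.4.11 of both 2021 SAPs. The direction is certain relative to the same rule without the new-therapy date: the failure curve is too high or unchanged, and its quantiles too early or unchanged. The supported size is about 0.3 to 2.7 percentage points at 12 months. That rests on the assumed hazards, treatment durations and shares above, and on new therapy starting within 30 days after the last dose. It would be larger only if surgery or radiotherapy counted as new therapy while dosing continued, which section 2.8.4.11 does not say.

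Three things are unaffected: the final analyses under the 2023 SAPs, LGG crossover within 30 days of the last dose (events and censoring already stop together there), and the planned median among patients who had the event.

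**What to change.** Delete the entry "new anticancer antineoplastic therapy start date" from section 2.8.4.11 of the HGG SAP Amendment 2 and the LGG SAP Amendment 1, as the 2023 SAPs do. Events and censoring then share one window, to 30 days after the last dose.

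If follow-up is meant to stop at new therapy, apply that to everyone: an AESI that begins after new therapy is not an event, and the text states whether surgery and radiotherapy count. The LGG crossover rule in section 2.1.1 is a model for this.

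Then rerun the primary AESI time-to-onset outputs. Alternatively, rely on the final-analysis versions and state in the report that the two were produced under different censoring rules. The cost is one line of wording and a rerun of those outputs; no new data are needed.
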